Aim 2 and Exploratory Aim. We will employ an intent-to-treat (ITT) approach by including all participants recruited into the study regardless of compliance. Every effort will be made to collect all outcome measures even if a participant does not engage in assigned treatments. Analysis of covariance (ANCOVA) will be used to compare study groups with respect to mean changes in each outcome from baseline to 12 weeks with baseline adjustment. Data from these analyses will provide estimated means, standard errors, and preliminary effect sizes for the *Fit2ThriveMB* intervention. These data will be used for future sample size calculations, to identify a primary endpoint and further refine the *Fit2ThriveMB* intervention to be tested in a more definitive trial. We will also use regression models to explore the relationship between changes in each outcome and intervention adherence. This study is not designed to make conclusions about *Fit2ThriveMB* efficacy without further study.

Timeline

The overall duration of the study will be 2 years, and each participant will be actively participating for 12 weeks.

10.0 Research with Vulnerable Populations:

Non-English Speaking Subjects: N/A

Subjects who are not yet adults (infants, children, teenagers): N/A

Cognitively Impaired Adults: N/A

Adults Unable to Consent: N/A

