Though not part of the intervention, participants may choose to keep the *Fit2thriveMB* study app on their phones and continue to use it. The functionality of the app depends on data collection. Data will continue to be collected after the conclusion of the 12 week intervention if a participant chooses to keep and use the app. Data collected includes: login frequency, app usage, data entered into the app including symptom burden, goal selection and physical activity and data transmitted from the Fitbit, including physical activity and steps taken. The app will remain functional and data will be collected for 12 months after the participant completes the initial 3 month intervention. The data is collected and stored for the purpose of analyzing post-intervention app usage and physical activity patterns. At the end of 12 months the app will no longer function. Participants will be provided with written instructions on how to remove the app if they wish during the 12 week functional performance video conference. Once the app is removed we will be unable to collect any data from their phone.

Coaching Calls

Fit2ThriveMB intervention participants will receive weekly coaching calls which will: a) provide feedback on the previous week’s symptom burden and progress on PA goals; b) review personalized goals and strategies for increasing PA for the next week; c) provide instruction on effective behavioral change techniques (see **Table 1 for listing of topics to be covered**) and d) inquire about any issues or injuries. Participants will be instructed to call or email their coach throughout the week if they encounter any issues. Coaching calls will be semi-structured and recorded to ensure fidelity. Coaching calls are expected to last from 10-15 minutes each.

Education Control

Participants assigned to this condition will be instructed to go about their usual activities and will receive education about PA and a healthy lifestyle for MBC patients. They will be encouraged to download the free Cancer.Net app which contains a Metastatic Breast Cancer Coach module. The Cancer.Net App content includes information about health and well-being, treatment guidelines specific to their cancer type medication and symptom tracking, a spot to save questions for future appointments and an appointment calendar.

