At the end of the 12 week intervention, participants in the education control group will receive a Fitbit and have access to the *Fit2ThriveMB* study app. If they choose to download the app and use it, the app will collect data including: login frequency, app usage, data entered into the app including symptom burden, goal selection and physical activity and data transmitted from the Fitbit, including physical activity and steps taken. This data will be collected for 12 months and stored for the purpose of analyzing post-intervention app usage and physical activity patterns. At the end of 12 months the app will no longer function. Participants will be instructed in how to download, and provided with written instructions for removing the app, if they wish following the 12 week assessment. Once the app is removed we will be unable to collect any data from their phone.

Support Calls

To match *Fit2ThriveMB* contacts, participants will also receive weekly calls that will cover health and well-being topics (see Table 3). They will be provided with the Fitbit after completion of week 12 assessments.

Table 3: Healthy Living Control Coaching Call Content

| Week | Theme |
|------|--|
| 1 | Mindfulness |
| 2 | Social Support: Friends, Family, Counseling and Support Groups |
| 3 | Social Support: Online Communities |
| 4 | Symptom Tracking |

| | |
|----|---|
| 5 | Art Therapy/Doing Activities you Enjoy (focus on quality of life) |
| 6 | Sleep |
| 7 | Fatigue |
| 8 | Cognition |
| 9 | Hydration |
| 10 | Nutrition |
| 11 | Healthy Grocery Shopping |
| 12 | Stress Management |

Study Retention Plan

To minimize attrition, study staff will develop good rapport with participants during recruitment and maintain the relationship throughout the study (e.g., by sending birthday cards). Participants will be provided with a phone number to call immediately if they encounter issues with any aspect of the intervention. Staff will convey reminders of scheduled assessments by phone, email, or text message, per participant preference. Participants will also be incentivized to complete assessments (\$41.50 at baseline and 12 weeks) for a total of \$83.00. Participants will be paid \$40.00 for completing the assessments in their entirety, and will be paid an additional \$1.50 at each time point to cover the cost of transferring the electronic payment to a personal checking account, if the participant chooses. Also, participants will receive a free Fitbit.

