| Social Support Exercise (SSE) | X | X | X |
| Sitting Time Questionnaire (STQ) | X | X | X |
| Process Evaluation | | | X |
| COVID-19 Assessment | X | X | X |
| Weight | X | | X |
| Blood Pressure | X | | X |
| SPPB | X | | X |
| Senior Fitness Test | X | | X |
| 6 minute Walk | X | | X |

Data quality control/checking

The majority of data is collected (PA, symptoms, acceptability) or uploaded electronically. The quality of these data will be checked by examining descriptive statistics and score ranges of all variables for missing and/or erroneous values. All data will be examined for violation of basic statistical assumptions (i.e. normality, multicollinearity) and transformed, if needed. Participants will be asked to complete all assessments, regardless of group assignment or adherence. Strategies for handling missing data (i.e. maximum likelihood estimation, multiple imputation) will be chosen based on the type and extent of the problem.

Statistical Analyses Plan

Aim 1. Feasibility and acceptability will be analyzed using descriptive statistics (frequencies, means and standard deviations). Feasibility will primarily be evaluated using the “successful completion rate” defined as: a) $\geq 80\%$ of MBC patients who enroll in the intervention will remain in the intervention and b) MBC patients will adhere to daily goals and wear Fitbit $\geq 70\%$ of study days (i.e. $\sim 59/84$ days) If a successful completion rate is achieved, *Fit2ThriveMB* will be deemed feasible. Additional measures of feasibility, fidelity, acceptability and safety will also be summarized and considered with the “successful completion” rate before proceeding with a more definitive trial.

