This study is classified as minimal risk because the probability and magnitude of harm or discomfort anticipated is not greater than those ordinarily encountered in daily life or during the performance of routine physical and psychological examinations or tests and confidentiality is adequately protected. The PI and study investigators will conduct continuous review of data and patient safety. Any staff member or investigator can spontaneously identify an adverse event. Participants will be instructed to call or e-mail the PI in the event of any emergencies or medical events within 24 hours of the event occurring. These instructions will be included in all cover letters that accompany study materials and displayed prominently within the app.

Events may also be spontaneously reported to staff during contact time. Adverse events and serious adverse events may also be identified during regularly scheduled calls or emails by researchers blinded to the treatment condition of the participant. These phone interviews or emails will be conducted every 4 weeks throughout the

12 week study period. Participants will be asked to complete the Non-spontaneous Adverse Events Questionnaire either via REDCap or via an interview with study staff. This form will be completed for all metastatic breast cancer survivor participants and will query the participant as to whether they have had any health and/or medical problems during the preceding 4 week period. Participants will be called or emailed until a response is received. Participants will also be required to provide the investigators with at least one emergency contact to have on file in the event we are fail to reach the participant after 5 or more attempts. If participant reports “YES” to item 5A-5D (see REDCap form), an adverse event form will be filed with the IRB.

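### Weekly injury questions are specified for the intervention calls only, and all events share one log without a source field, so recorded adverse events may look more frequent in the intervention arm

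*Combined protocol and SAP*

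**What the plan says.** **Intervention calls.** Section 9.0, Coaching Calls, says that "intervention participants will receive weekly coaching calls which will" do four things. The last is to "inquire about any issues or injuries". The calls are described as semi-structured.

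**Control calls.** Section 9.0, Support Calls, gives the control arm the same number of contacts and says that "participants will also receive weekly calls that will cover health and well-being topics". Table 3 lists one theme per week. Neither the text nor the table mentions injuries or adverse events.

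**Common questionnaire.** Section 21.0 adds a scheduled check in both arms, the Non-spontaneous Adverse Events Questionnaire, with contacts by researchers who do not know the allocation. "These phone interviews or emails will be conducted every 4 weeks", and "This form will be completed for all metastatic breast cancer survivor participants". It asks whether participants "have had any health and/or medical problems during the preceding 4 week period". Non-responders are pursued until they answer.

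**Pooling and use.** Section 21.0 also accepts events volunteered to staff in any contact. Every identified event goes into one log that holds the participant's identity, the date and a description. In the Statistical Analyses Plan under Aim 1, "Additional measures of feasibility, fidelity, acceptability and safety will also be summarized" and weighed with the completion rate before a definitive trial. The plan does not say which source of events that summary uses.

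**The concern.** The arms are matched on number of calls but, as written, not on whether the caller asks about harm. Some events that a participant would not volunteer, and would not recall on a form covering four weeks, will be picked up by a direct weekly question. If that question is asked in one arm only and its yield is pooled with everything else, the log compares reporting intensity as well as harm.

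This matters for two reasons. The safety summary is part of what the investigators will weigh before a larger trial, and in a pilot of 50 an event or two can colour it. Under-asking in the control arm may also leave events unrecorded in women with metastatic disease, which removes the background rate against which intervention-arm events would be read.

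**Working it through.** The plan states no adverse-event rate, detection rate or safety power, so there is no figure of its own to reproduce. The check is an illustration under equal true risk.

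**Inputs from the documents**
- 25 participants per arm (Section 4.0).
- Twelve weekly calls in each arm (Section 9.0, Tables 1 and 3), with an injury inquiry described for the intervention arm only.
- A common questionnaire every 4 weeks with a 4-week recall window (Section 21.0): 12 / 4 = 3 forms, which together span the study.

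**Inputs assumed, because the documents give none**
- q, the share of events captured by the 4-weekly form, taken as equal in both arms: 0.60 to 0.80.
- r, the share of events missed by the form that the weekly question picks up: 0.30 to 0.50.
- Extra capture on control calls: zero at first, relaxed below.
- True risk p over 12 weeks: 20%.

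**Formulas**
- Control, observed: p × q.
- Intervention, observed: p × [1 − (1 − q)(1 − r)].
- Ratio: [1 − (1 − q)(1 − r)] / q, which does not depend on p.

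**Results** (25 × 0.20 = 5 participants with a true event per arm)

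| q | r | Control capture | Intervention capture | Ratio | Expected participants recorded, control vs intervention |
|---|---|---|---|---|---|
| 0.80 | 0.30 | 0.80 | 1 − 0.20 × 0.70 = 0.86 | 1.075 | 4.0 vs 4.3 |
| 0.80 | 0.50 | 0.80 | 1 − 0.20 × 0.50 = 0.90 | 1.125 | 4.0 vs 4.5 |
| 0.60 | 0.30 | 0.60 | 1 − 0.40 × 0.70 = 0.72 | 1.20 | 3.0 vs 3.6 |
| 0.60 | 0.50 | 0.60 | 1 − 0.40 × 0.50 = 0.80 | 1.33 | 3.0 vs 4.0 |

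**Sensitivity to the assumptions**
- Complete form (q = 1) or unproductive weekly question (r = 0): ratio 1.00.
- q = 0.90 with r from 0.30 to 0.90: ratio 1.03 to 1.10.
- q = 0.50 with r = 0.90: 0.95 / 0.50 = 1.90, the widest case examined.
- Control calls pick up half as much as the direct question (r/2): at q = 0.80, r = 0.30, control capture is 1 − 0.20 × 0.85 = 0.83 and the ratio 0.86 / 0.83 = 1.04. At q = 0.60, r = 0.50, it is 1 − 0.40 × 0.75 = 0.70 and the ratio 0.80 / 0.70 = 1.14.
- True risk of 40% instead of 20%: the ratios stay the same and the counts double, so the largest gap in the table becomes 6.0 vs 8.0.

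**After the change.** With the same question in both arms, numerator and denominator are equal and the ratio is 1.00 for every q and r. With the comparison restricted to the common form, it is q / q = 1.00.

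**The case against.** The case for leaving the plan alone is substantial, and most of it limits the size of the point.

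- **The common questionnaire is a strong safeguard.** It reaches everyone, covers all 12 weeks, is run by blinded researchers and is chased to completion. This stands: if it is near-complete, the imbalance is near zero. But chasing secures a returned form, not full recall, and the plan does not restrict the safety summary to it.
- **The control side rests on silence.** The description is short, and Table 1, the intervention's own schedule, does not list the injury inquiry either. Control callers may already ask. If so, the sponsor need only write it down.
- **Controls have other reporting routes.** They have weekly staff calls, some on symptoms, sleep and fatigue. Cover letters tell them to report medical events, and they have the study website. A reader might count 15 prompts (12 calls plus 3 forms) against 3 and take that as the imbalance in detection. The documents do not support that, because unprompted reports on control calls also count.
- **The adverse-event definition is narrow.** Section 21.0 requires an event to be unexpected, at least possibly related, and indicative of greater risk than was known. Section 19.0 already names soreness, strains and worsened arthritis as possible risks. Many minor injuries raised on coaching calls may never qualify. The definition does not, however, equalise detection of those that do.
- **No between-arm safety test or threshold is planned.** Feasibility rests mainly on completion and adherence. This stands, and so does the remark that the bias, if present, makes the intervention look less safe rather than safer.

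Asking about injuries while coaching inactive patients to do more is sensible. The point is only that the question is not described for both arms and its yield is not separated.

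**Conclusion.** The point holds in a limited form. As written, prompting about harm is unequal between arms, and its results enter a pooled log with no source field. Recorded adverse events may therefore look more frequent in the intervention arm at equal true rates. Under the model used, the ratio is never below 1.

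The size cannot be known from the documents. It is nil if the 4-weekly form is complete. It is about 7.5% to 33% under the stated assumptions, including no extra capture on control calls, or one participant or fewer at 25 per arm and 20% true risk. The consequence is for a descriptive summary that feeds the decision on a definitive trial.

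A reader might go further and conclude that events will appear more frequent, or that coaches follow a scripted injury inquiry. Neither is supported: the shared questionnaire could remove the difference, and the coaching calls are only semi-structured. The change is still worth making, because it is cheap and following the plan to the letter leaves the ambiguity in place.

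**What to change.** 1. In Section 9.0, Support Calls, add the same issue-and-injury question to each weekly control call, in the same words as on the coaching calls.
2. In Section 21.0, add a source field to the adverse-event log (4-weekly questionnaire, weekly call, other contact).
3. In the Statistical Analyses Plan, state that any between-arm safety summary is based on the Non-spontaneous Adverse Events Questionnaire, and that events found only through other contacts are listed separately by arm.

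Steps 1 and 3 support each other: having discussed an injury on a call could make a participant more likely to report it on the form, so the form alone is cleanest when the calls also match. If the calls cannot be changed, steps 2 and 3 are still available.

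The cost is one question per control call, one column in the log, and slightly more events to record. No extra staff or new data collection is needed.

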
3.0 Inclusion and Exclusion Criteria:

Inclusion criteria:

- Female; ≥ 18 years of age
- Diagnosed with metastatic breast cancer or locally advanced disease not amenable to surgical resection (Metastases to the auxiliary lymph nodes, and nowhere else in the body, do not qualify).
- Fluent in spoken and written English
- Own a smartphone
- Have access to the internet to complete assessments

- Self-report engaging in <150 minutes of moderate to vigorous PA per week.

Exclusion criteria:

- Untreated brain metastases
- Breast cancer with metastases to only the auxiliary lymph nodes.
- Uncontrolled cardiovascular disease or other major contraindications (i.e. non-ambulatory, severe cognitive or functional limitations) to PA participation
- Current enrollment in another dietary or PA trial

All MBC patients must obtain medical clearance from their oncologist to participate.

Adults unable to consent/Cognitively Impaired, individuals who are not yet adults (under 18 years of age), pregnant women and prisoners or other detained individuals will NOT be included in the present study.

4.0 Sample Size:

We will recruit 50 metastatic breast cancer patients to participate in this study. Sample size calculations (n=50) are based on the successful completion rate defined as: a) an attrition rate of $\leq 20\%$ (i.e. complete 12 week assessment) and b) adherence to daily goals and wearing Fitbit $\geq 70\%$ of study days (i.e. $\sim 59/84$ days). With half of participants (n=25) assigned to each condition, there is $>85\%$ power to differentiate between a 60% (control) and 80% (*Fit2ThriveMB*) “successful completion” rate with a one-tailed, exact test for binomial proportion at a 0.05 significance level (SAS V9.4).

5.0 Recruitment and Screening Methods:

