Participants will be recruited from the following sites, all affiliated with Northwestern University Feinberg School of Medicine and the Lurie Comprehensive Cancer Center, or additional Northwestern Medicine sites : a) outpatient facility at Galter Pavilion of Northwestern Memorial Hospital; b) Lynn Sage Comprehensive Breast Cancer Center at Prentice Women’s Hospital; and c) additional Northwestern Medicine Cancer Center locations (e.g. Cancer Center at Northwestern Medicine Lake Forest Hospital, Northwestern Medicine McHenry Hospital Cancer Center, Northwestern Medicine Cancer Center Delnor). For all methods, we will consult with patient’s oncologists on an as needed basis to help determine if potential patients are good potential candidates for participation.

Screening

Participants will complete initial eligibility screening online or over the phone. It will take approximately 15 minutes. Screening will include evaluation of eligibility, the Physical Activity Readiness Questionnaire (PAR-Q)²⁰, which assesses cardiovascular disease history, symptoms, risk factors, and other health issues and the Fall Risk Assessment Questionnaire (FRQ)²¹, which identifies individuals who may be at risk for falling. Screening will also include questions regarding technology and equipment the women currently have at home that may be usable for the baseline and week 12 functional performance video conference assessments. All women will also be required to obtain medical clearance from their oncologist.

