Short Physical Performance Battery (SPPB). Participants will also complete the Short Physical Performance Battery (SPPB), a well-validated physical function performance measure.³¹⁻³³ The SPPB score is based on timed measures of gait speed, ability to rise from a chair, and standing balance. Gait speed will be measured using the better of two recorded times over a 4-meter course. Chair stand time will be measured as the time needed to rise five times from a seated position in a chair, with arms folded across the chest. For the balance test, participants will be asked to maintain their feet side-by-side, semi-tandem, and tandem positions for 10 seconds each. Each individual performance measure will be scored according to established cutpoints^{31,33} and aggregated for a total SPPB score.

Senior Fitness Test.³⁴ We will use several items from the Senior Fitness Test including a) the 8-Foot Up-and-Go, a test of physical agility and dynamic balance, which measures the speed at which an individual walks around a cone or other object 8 feet away and back; b) the Arm Curl test, which assesses arm muscle strength endurance, specifically of the biceps, by measuring the number of arm curls that can be completed using a 5 lb weight in 30 seconds; c) and the 2 Minute Step Test, an aerobic endurance test, which counts the number of full in-place steps completed in two minutes. Participants will also complete a 30- second one leg stand test on each side (right and left) where they are instructed to stand on one foot for up to 30 seconds and timed.

6 minute walk.³⁵ MBC patients will complete a 6 minute walk test to assess their submaximal level of functional capacity. The goal is for the participant to walk as far and she can during these 6 minutes. Distance is measured once the 6 minute walk is complete, and provides information regarding cardiopulmonary and musculoskeletal systems that are used during physical activity that points toward exercise tolerance. Participants will be instructed to wear the accelerometer and a pedometer for the duration of the 6 minute walk test and will be instructed in the use of the provided blood pressure monitor and heart rate monitor.

Additional Exploratory or Confounding Variables

Demographics/Health History. Participants will self-report demographic information (i.e. age, race) and health history.

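### The plan times the 4-meter walk and five chair stands but specifies only a cut-point-scored SPPB total; the two times should be added as continuous exploratory outcomes

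*Combined protocol and SAP*

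**What the plan says.** Section 9.0, Measures, Functional Performance, describes the battery this way: "The SPPB score is based on timed measures of gait speed, ability to rise from a chair, and standing balance".

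- **Gait:** "Gait speed will be measured using the better of two recorded times over a 4-meter course".
- **Chair stands:** "Chair stand time will be measured as the time needed to rise five times from a seated position in a chair".
- **Balance:** participants are asked to "maintain their feet side-by-side, semi-tandem, and tandem positions for 10 seconds each", so this component is capped by design.
- **Scoring:** "Each individual performance measure will be scored according to established cutpoints". The component scores are then added to give the total. The cut-points are cited but not printed.

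Functional performance at 12 weeks belongs to Aim 3. The Statistical Analyses Plan (Aim 2 and Exploratory Aim, which I take to cover Aim 3) compares the arms on change in each outcome by ANCOVA with baseline adjustment. It says the estimates will serve future sample size calculations and the choice of a primary endpoint. It does not list the gait or chair-stand times as outcomes.

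**The concern.** Both times are continuous when recorded, but the only SPPB result specified is a total built from a few ordered categories. A woman who becomes faster without crossing a cut-point shows no change on that component. A woman already in its top category cannot improve on it at all.

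The pilot exists partly to estimate effect sizes. If categorisation weakens the SPPB effect, lower-limb function could look less responsive than it is when the next endpoint is chosen. If the times are analysed only after the totals have been seen, that analysis will be post hoc.

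**Working it through.** **Inputs from the documents.** There are 50 women, 25 per arm (section 4.0). Attrition of at most 20% leaves 50 × 0.80 = 40 completers. Gait and chair stands are timed, and the analysis is baseline-adjusted ANCOVA (section 9.0).

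**Not in the documents.** The cut-points, the number of categories, the share of women at the top, and the SD, effect and correlation of the times are not given. The plan states no SPPB figure, so there is none to reproduce. What follows is illustration under stated assumptions.

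**Step 1: one component.** Take a normally distributed time, signed so that higher is better, in SD units. The raw time carries information 1 per woman about a small shift. Grouped at cut-points c, it carries

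I = Σ [φ(c_{k−1}) − φ(c_k)]² / p_k.

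Assume four categories, with the women below the top split evenly over the other three.

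- With 50% at the top, the cut-points are −0.967, −0.431 and 0, and the category shares are 0.1667, 0.1667, 0.1667 and 0.5. The density differences are −0.2499, −0.1137, −0.0353 and 0.3989. I = 0.3746 + 0.0776 + 0.0075 + 0.3183 = 0.778.
- With 90% at the top, I = 0.1653 + 0.0910 + 0.0640 + 0.0342 = 0.3545.

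| Share in top category (assumed) | Information kept, one component | 50 women × that share |
|---|---|---|
| 25% | 0.861 | 43 |
| 50% | 0.778 | 39 |
| 70% | 0.636 | 32 |
| 80% | 0.522 | 26 |
| 90% | 0.355 | 18 |

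An ANCOVA treats the categories as integer scores, which keeps slightly less: 0.77, 0.62, 0.50 and 0.34 at 50%, 70%, 80% and 90%.

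**Step 2: a sum of components.** The plan analyses a total, so step 1 does not describe it. Take two such scores from times correlated 0.5, both shifting equally, and ignore balance (all assumed). With b the change in mean score per unit shift, v the score variance and cov the covariance between scores, efficiency relative to one raw time is (2b)² / (2v + 2cov).

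At a 50% top share, b = 1.012, v = 1.333 and cov = 0.546, so the efficiency is 4.100 / 3.758 = 1.09. At 70%, 80% and 90% it is 0.91, 0.76 and 0.53. The sum therefore recovers part of the loss, and at 50% it slightly beats a single raw time.

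The like-for-like comparator is the sum of the two raw times, whose efficiency is 4 / (2 + 2 × 0.5) = 1.333. Dividing by that gives 1.09/1.333 = 0.82, then 0.68, 0.57 and 0.40. The cost of grouping remains.

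**Step 3: under ANCOVA.** I use a simulation of one component with 20,000 runs, two-sided 0.05, an assumed baseline to 12-week correlation of 0.7 and an assumed effect of 0.5 SD.

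| | Continuous time | Four-level score: 25% at top | 50% | 70% | 85% |
|---|---|---|---|---|---|
| Power, 40 completers | 57% | 43% | 35% | 24% | 11% |
| Power, all 50 | 67% | 52% | 42% | 30% | 16% |

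With 40 completers and effects from 0.3 to 0.8 SD, power on the continuous time runs from 25% to 93%. On the four-level score it runs from 19% to 81% with 25% at the top, and from 7% to 19% with 85% at the top.

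**The case against.** A reader might infer that these women were screened for adequate function, so that a ceiling is certain. The documents do not support that. Section 3.0 excludes uncontrolled cardiovascular disease and "other major contraindications (i.e. non-ambulatory, severe cognitive or functional limitations) to PA participation", but sets no minimum level of function. Oncologist clearance is permission to take part, not a performance standard. The fall-risk questionnaire, "which identifies individuals who may be at risk for falling", has no stated exclusion threshold. Two facts point the other way: only women reporting under 150 minutes of moderate to vigorous activity a week are enrolled, and section 2.0 describes the population as having more functional decline.

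A reader might also infer that the times are thrown away. Section 22.0 keeps the test sheets, scans them and enters them in REDCap, and nothing bars analysing the times. What is missing is a specified analysis.

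A third tempting reading is that the total should give way to the times. The total is the established scoring of a validated battery, and step 2 shows it can match or beat a single raw time at a moderate top share. Demoting it is not justified.

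Finally, Aim 3 does not rest on the SPPB. The 6-minute walk, 8-foot up-and-go, 2-minute step, arm curl and one-leg stand are not described as cut-point scored. The plan's data checks on score ranges would probably show a pile-up at the maximum, and the study disclaims conclusions about efficacy.

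All of this stands and limits the importance of the point. It does not supply the missing analysis. None of the other tests directly duplicates the five-chair-stand time, and estimating effects for the next trial is what these analyses are for.

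**Conclusion.** This is a cheap improvement, not an error in the plan. The text establishes that two continuous times are collected, that the only SPPB result specified is a cut-point-scored total, and that no analysis of the times is named. Grouping loses information at any top share: for one component in four assumed categories, about 14% is lost with 25% of women at the top and about 65% with 90%. Those figures rest on a normal time, a small shift, four categories and an even split of the lower three. They must not be read as the loss in the planned total, or as an effective sample size for it. How far a ceiling adds to the loss in this trial cannot be determined from the documents.

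**What to change.** 1. In section 9.0, Functional Performance, name 4-meter gait speed (4 m divided by the better time) and five-chair-stand time as continuous exploratory outcomes.
2. In the Statistical Analyses Plan, put both under the same baseline-adjusted ANCOVA as the other outcomes.
3. Keep the SPPB total and its ANCOVA as planned.
4. Report the percentage of women at the maximum SPPB score at baseline, by arm. This replaces the unknown ceiling share with an observed one.

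The cost is two more rows in the functional-performance results and two more exploratory estimates to interpret with restraint. No new data collection is needed.
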